9 ASSESSMENT OF INVESTIGATIONAL MEDICINAL PRODUCT

9.1 PRIMARY ENDPOINT

The primary endpoint is the change from baseline in serum phosphorus level at Week 8.

The baseline of serum phosphorus value will be the last serum phosphorus level obtained before the first double-blind IMP dosing.

The serum phosphorus at Week 8 will be the serum phosphorus level obtained within the Week 8 analysis window.

All serum phosphorus values (scheduled or unscheduled) may be used to provide a value for the primary endpoint if appropriate according to above definition. The analysis window used to allocate a time point to a measurement will be defined in the Statistical Analysis Plan (SAP).

9.2 SECONDARY ENDPOINTS

- The change from baseline in total cholesterol at Week 8
- The change from baseline in LDL-C at Week 8
- The change from baseline in calcium-phosphorus product at Week 8
- The change from baseline in iPTH level at Week 8
- Percentage of patients reaching the target serum phosphorus level (4.6 mg/dL [1.49 mmol/L], inclusive) at Week 8
- The change from baseline in serum phosphorus level at Week 4

9.3 SAFETY ENDPOINTS

- Proportion of patients with adverse events
- Clinically significant changes in vital signs and clinical laboratory parameters

Observation period

The observation of safety data will be as follows:

- Pre-treatment period: The pre-treatment observation period is defined from the signed informed consent up to the first dose of double-blind IMP.
- Treatment Emergent Adverse Event (TEAE) period: The TEAE observation period is defined as the time from the first dose of double-blind IMP to the last dose of double-blind IMP+3 days.

- Post-treatment period: The post-treatment observation period is defined as the time starting the day after the end of the TEAE period up to the end of the study (see definition in [Section 6.2.1](#)).

9.3.1 Adverse events

All AEs diagnosed by the Investigator will be reported and described.

All AEs will be coded to a “Lowest level term (LLT)”, “Preferred term (PT)”, “High level term (HLT)”, “High level group term (HLGT)” and associated primary “System organ class (SOC)” using the version of Medical dictionary for regulatory activities (MedDRA) currently at Sanofi at the time of the considered database lock.

Refer to [Section 10.4](#) to [Section 10.7](#) for details.

9.3.2 Laboratory safety variables

The clinical laboratory data consist of hematology (complete blood count [CBC], differential, platelet and prothrombin time), chemistry (serum phosphorus, calcium [adjusted for albumin], albumin, calcium-phosphorus product, chloride, bicarbonate, uric acid, sodium, potassium, glucose, blood urea nitrogen [BUN], alanine aminotransferase [ALT], aspartate aminotransferase [AST], creatinine), and lipid panel (total cholesterol, LDL-C, high-density lipoprotein cholesterol [HDL-C], non-high-density lipoprotein cholesterol [non-HDL-C] and triglycerides).

Clinical laboratory values will be analyzed after conversion into standard international units. International units will be used in all listings and tables.

9.3.3 Vital signs

Vital signs include: heart rate (HR), systolic blood pressure (BP) and diastolic BP, and body temperature in sitting position.

10 STUDY PROCEDURES

10.1 VISIT SCHEDULE

For all visits after Day 1/Week 0 (randomization visit), a timeframe of ± 3 days will be allowed.

For all visits after Day 1/Week 0 (randomization visit), if one visit date is changed, then the next visit should take place according to the original schedule as outlined [Section 1.2](#).

Laboratory tests:

The laboratory data are collected in accordance with the study schedule in [Section 1.2](#):

- Hematology
- Chemistry
- Serum pregnancy test

NOTE: Any clinically relevant abnormal laboratory value should be immediately rechecked for confirmation before making any decision for the concerned patient. It should be documented as an AE/SAE as applicable. Please also refer to [Section 10.4](#).

According to the discretion of the Investigator for safety concern, the relevant laboratory parameters (eg, serum potassium) can be tested at any scheduled visit or unscheduled visit if necessary.

Decision trees for the management of certain laboratory abnormalities by Sanofi are provided in [Appendix A](#).

Physical examination:

A general physical examination should be performed at the time points indicated in the study flowchart in [Section 1.2](#). If a new clinically significant abnormality or worsening from baseline is detected after randomization, then an AE should be reported and the patient should be considered for further clinical investigations and/or specialist consultation as per the Investigator's medical judgment.

Blood pressure / heart rate:

Blood pressure should be measured in sitting position under standardized conditions, approximately at the same time of the day, on the same arm, with the same apparatus (after the patient has rested comfortably in sitting position for at least five minutes). Values are to be recorded in the e-CRF; both systolic BP and diastolic BP should be recorded. At the first Screening Visit, BP should be measured in both arms. The arm with the highest diastolic pressure will be determined at this visit, and BP should be measured on this arm throughout the study. This highest value will be recorded in the e-CRF.

Heart rate will be measured at the time of the measurement of BP.

NOTE: in case of high BP values at Screening Visit, the Investigator is responsible for the optimization of the patient's treatment to achieve BP targets as defined by local guidelines.

Body weight and height

Body weight should be obtained with the patient wearing undergarments or very light clothing and no shoes, and with an empty bladder. The same scale should be used throughout the study.

The use of calibrated balance scales is recommended, if possible. Self-reported weights are not acceptable; patients must not read the scales themselves.

Height needs to be measured as self-reported heights are not acceptable.

10.1.1 Screening Period

The screening period will take place up to 4 weeks or 28 days (and as short as possible, upon receipt of laboratory eligibility criteria) prior to randomization/Day 1 visit. Eligible patients who are taking phosphate binder(s) at Screening Visit will enter a 2-week phosphate binder washout period. Eligible patients who are not taking phosphate binder(s) at screening visit will proceed to the start of the 8-week treatment period (Day 1).

10.1.1.1 Screening Visit (Visit 1/Week -4 /Day -28 up to -19 for patients on phosphate binder[s] and Visit 1/Week -1.5/Day -10 to -1 for patients not on phosphate binder[s])

- Complete informed consent - the patient will receive complete information about the study both verbally and in writing. Written informed consent for the study must be obtained prior to any study-related investigations.
- Assess inclusion/exclusion criteria.
- Obtain patient demography – age and gender.
- Obtain medical history (including menopausal status) and renal history.
- Document prior medication (prescription and non-prescription medication) history within the last 30 days, especially for phosphate binder(s) treatment.
- Record concomitant medication (prescription and non-prescription medication).
- Physical examination.
- Take vital signs including HR, BP and body temperature.
- Get body weight and height measurements.
- Contact IVRS/IWRS for notification of Screening Visit. Patient number will be allocated by the IVRS/IWRS. This patient number is composed of a 12-digit number containing the 3-digit country code, the 4-digit center code and the 5-digit patient chronological number

(the 5-digit patient chronological number is 00001 for the first patient screened in a center, 00002 for the second patient screened in the same center).

- Collect AEs from this point onward:

All AEs and SAEs will be collected from the time of informed consent signature and throughout the study until the post Follow-Up visit.

- Obtain blood sample for:
 - Hematology: CBC, differential, platelet and prothrombin time.
 - Chemistry: calcium (adjusted for albumin), albumin, calcium-phosphorus product, chloride, bicarbonate and creatinine.
 - Serum phosphorus.
 - Serum iPTH.
 - Serum 25-hydroxy vitamin D.
 - Serum pregnancy test (women of childbearing potential only).
 - Calculate and record estimated Glomerular Filtration Rate (eGFR) based upon screening values using Modification of Diet in Renal Disease (MDRD) formula:
$$\text{eGFR (mL/min/1.73 m}^2\text{)} = 175 \times (\text{serum creatinine [mg/dL]})^{-1.154} \times (\text{Age [years]})^{-0.203} \times (0.742, \text{if female})$$
- Inform patient who are taking phosphate binder(s) to discontinue their current phosphate binder(s) for 2 weeks (washout period). These patients will return for their V1a (Day -10 to -1).
- An appointment will be given for the next visit.

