7.2.2 Exclusion criteria related to the current knowledge of Sanofi compound

E 10. Have known hypersensitivity to sevelamer or any constituents of Renvela tablets.

E 11. Have bowel obstruction, active dysphagia, swallowing disorder, a predisposition to or current bowel obstruction, ileus, or severe gastrointestinal motility disorders including severe constipation.

E 12. Using or plan to use anti-arrhythmic or anti-seizure medications for arrhythmia or seizure disorders.

E 13. Is pregnant or breast-feeding.

E 14. If the patient is female, and of childbearing potential (such as pre-menopausal and not surgically sterile, postmenopausal women who are amenorrheic for less than 12 months), is not willing to use an effective contraceptive method throughout the study.

E 15. Have any condition, which in the opinion of the investigator would prohibit the patient's inclusion in the study.

7.2.3 Additional exclusion criteria during or at the end of screening or washout period before randomization

E 16. Patient who has withdrawn consent before randomization (starting from signed informed consent form).

E 17. Have serum phosphorus measurement <5.5 mg/dL (1.78 mmol/L) at Screening Visit (if patients are not on phosphate binder[s] at Screening Visit) **OR** at the end of Washout Period (if patients are on phosphate binder[s] at Screening Visit).

Re-screening:

Patients who are screened and failed to fulfill the inclusion or exclusion criteria could be re-screened if their screening central lab results are as follows:

- serum phosphorus levels >4.6 mg/dL (1.49 mmol/L)

Re-screen is not advised within 1 month of the prior screening attempt. All patients re-screened must sign a consent form prior to any re-screening activities taking place. The number of re-screening attempts will be limited to two. Careful consideration is necessary as to the appropriateness of multiple re-screening attempts. Patients should only be re-screened if their condition has progressed such that the treating physician believes that they may now be eligible and the patient is a willing participant. Patients who fail screening following wash out from their usual phosphate binder(s) may be prescribed these again at the physician's discretion. However the dose should be considered to be stabilized by the investigator prior to re-screening.

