10.1.1.2 Post-Washout visit (Visit 1a/Week -1.5/Day -10 to -1)

This visit is only applied for patients taking phosphate binder(s) at screening visit.

- Assess inclusion/exclusion criteria.
- Collect AEs.
- Record concomitant medication (prescription and non-prescription medication).
- Obtain blood sample for:
 - Chemistry: serum phosphorus.
- An appointment will be given for the next visit.

Note: For patients on phosphate binder(s), the time window of V1 and V1a is up to 10 days, respectively. However, the total time window of V1 and V1a should not exceed 14 days to ensure the screening period is up to 4 weeks, including a wash out period which should be 2 weeks (14 days).

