10.2 DEFINITION OF SOURCE DATA

Evaluations that are reported in the e-CRF must be supported by appropriately signed identified source documentation related but not limited to the following:

- Agreement, date, and signature of informed consent mentioning the study identification.
- Patient identification, last participation in a clinical trial, medical history, associated diseases, and data related to the studied pathology.
- Contraception methods for women of childbearing potential.
- Previous and concomitant medication.
- Study identification.
- Treatment number, dates of administration.
- Dates of visits and assessments including the examination report.
- Vital signs, height, body weight.
- Emailed central lab reports (dated and signed by the Principal Investigator or Subinvestigator).
- IVRS/IWRS confirmation email (screening, screen failure, training kit allocation, randomization, treatment reallocation, discontinuation, end of DBTP, end of study, unblinding if applicable).
- AEs and follow-up:
 - In case of SAE, the site should file in the source document at least copies of the hospitalization reports and any relevant examination reports documenting the follow-up of the SAE.
- Date of premature study discontinuation (if any) and reason.

Source documentation may be found in the following:

- Patient's identity.
- Medical history.
- Hospital records.
- Nursing notes.
- Physician's notes.

10.3 HANDLING OF PATIENT TEMPORARY OR PERMANENT TREATMENT DISCONTINUATION AND OF PATIENT STUDY DISCONTINUATION

The IMP should be continued whenever possible. In case the IMP is stopped, it should be determined whether the stop can be made temporarily; permanent IMP discontinuation should be a last resort. Any IMP discontinuation should be fully documented in the e-CRF. In any case, the patient should remain in the study as long as possible.

- Pregnancy in female participant will lead to definitive treatment discontinuation in all cases.

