10.3.3 List of criteria for permanent treatment discontinuation

The patients may withdraw from treatment with the IMP if they decide to do so, at any time and irrespective of the reason, or this may be the Investigator's decision. All efforts should be made to document the reasons for treatment discontinuation and this should be documented in the e-CRF.

Patients should discontinue the IMP for the following reasons:

- Pregnancy, intention for pregnancy, or no longer with effective contraceptive method of birth control (females only).
- Serious adverse event (or non-serious but severe in intensity) of hypersensitivity reaction considered related to IMP.
- At patient request.
- If, in the Investigator's opinion, continuation with the administration of the IMP would be detrimental to the patient's well-being.
- Intercurrent condition that requires discontinuation of the IMP (eg, laboratory abnormalities, please refer to decision tree [Appendix A](#)).

- At the specific request of the Sponsor.
- Any code breaking requested by the Investigator.
- Patient receives double-blind treatment prior to randomization.

In addition, if the patient requires dialysis (hemodialysis or peritoneal dialysis) or is admitted for renal transplantation at any time, he or she must be withdrawn.

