10.4.1.3 Adverse event of special interest

An AESI is an AE (serious or non-serious) of scientific and medical concern specific to the Sponsor's product or program, for which ongoing monitoring and immediate notification by the Investigator to the Sponsor is required. Such events may require further investigation in order to characterize and understand them. Adverse events of special interest may be added or removed during a study by protocol amendment. Please see [Section 10.4.4](#) and [Appendix A](#) for additional information.

- Pregnancy of a female subject entered in a study as well as pregnancy occurring in a female partner of a male subject entered in a study with IMP
 - Pregnancy occurring in a female patient entered in the clinical trial or in a female partner of a male patient entered in the clinical trial. It will be qualified as an SAE only if it fulfills one of the seriousness criteria (see [Section 10.4.1.2](#))
 - In the event of pregnancy in a female participant, IMP should be discontinued.
 - Follow-up of the pregnancy in a female participant or in a female partner of a male participant is mandatory until the outcome has been determined.
- Symptomatic overdose (serious or non-serious) with IMP/NIMP
 - An overdose (accidental or intentional) with the IMP/NIMP is an event suspected by the Investigator or spontaneously notified by the patient (not based on systematic pills count). Renvela is a non-absorbed drug, thus it is not possible to define a symptomatic overdose prospectively. However, the investigator may use his or her judgment to report an event that he or she considers to be a symptomatic overdose using the corresponding screens in the e-CRF using the Term "Symptomatic OVERDOSE (accidental [or intentional])". The patient should be monitored and appropriate symptomatic treatment instituted.

The circumstances of the overdose should be clearly specified in the verbatim.

Of note, asymptomatic overdose has to be reported as a standard AE.

- Increase in alanine transaminase (ALT) (see the "Increase in ALT" flow chart in [Appendix A](#) of the protocol).

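### The only scheduled pregnancy test is at V1, so the negative result is 19 to 28 days old at first dose for women on phosphate binders, against 1 to 10 days for other women

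*Protocol*

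**What the plan says.** Pregnancy has three consequences in the protocol. The criterion numbers below are those of Section 7.2.2; the synopsis numbers the same criteria E 11 and E 12.

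- **Exclusion.** Section 7.2.2: "E 13. Is pregnant or breast-feeding". Eligibility is assessed at V1 and again at V1a and V2 (Sections 10.1.1.2 and 10.1.2.1).
- **Stopping reason.** Section 10.3: "Pregnancy in female participant will lead to definitive treatment discontinuation in all cases". The list in Section 10.3.3 opens with "Pregnancy, intention for pregnancy, or no longer with effective contraceptive method of birth control (females only".
- **AESI.** Section 10.4.1.3 begins its list with "Pregnancy of a female subject entered in a study" and also covers female partners of male patients. Table 1 in Section 10.4.5 requires expedited reporting within 24 hours. SAP Section 2.1.4.1 repeats the definition, and SAP Section 2.4.5.1 tabulates treatment-emergent AESIs.

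The test appears once in the visit lists, at V1 (Section 10.1.1.1): "Serum pregnancy test (women of childbearing potential only". The matching row of flow chart 1.2 carries one mark. The blood lists for V1a, V2, V3 to V5, V6 and V7 do not include it. Section 10.1 names the test among the laboratory tests but ties them to the flow chart, so it adds no time point.

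The V1a blood list contains serum phosphorus only. Of V1a, Section 10.1.1.2 says: "This visit is only applied for patients taking phosphate binder(s) at screening visit".

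The protocol also relies on prevention. E 14 excludes a woman of childbearing potential who "is not willing to use an effective contraceptive method throughout the study".

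**The concern.** One exclusion criterion is checked with results of very different age, depending only on whether the woman was taking a binder at screening. A woman on binders is tested before her washout begins. She then returns for V1a, where blood is drawn and eligibility is reviewed, but the review of E 13 has no new result behind it. The same holds at V2. A conception around or after V1 could pass E 13 on the old negative, and the woman could be randomized and dosed.

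After Day 1 the stopping rule and the 24-hour AESI notification have no scheduled detection step. A restart after a temporary stop requires that the selection criteria are still met (Section 10.3.1), again with no pregnancy test named.

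What is at stake is participant safety and, to a smaller extent, the completeness of the pregnancy AESI count. The primary comparison is not affected.

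**Working it through.** **Inputs**

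- V1 window, patients on binders: Day -28 to -19 (Section 10.1.1.1).
- V1 window, patients not on binders: Day -10 to -1 (same section).
- V1a window: Day -10 to -1 (Section 10.1.1.2).
- First dose: V2, Day 1 (Section 10.1.2.1).
- End of treatment: V6, Day 57 ± 3 (Section 10.1.2.5).

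**Day count.** Section 10.1.1 caps screening at 28 days before Day 1. With no Day 0, the gap from Day -d to Day 1 is d days, so Day -28 to Day 1 is 28 days. This reproduces the protocol's figure. Counting a Day 0 would give 29, which does not match, so no Day 0 is used.

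**Age of the result at first dose** (gap = d)

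| Route | Sample carrying the test | Age at Day 1 |
|---|---|---|
| On binders, as planned | V1, Day -28 to -19 | 19 to 28 days |
| Not on binders, as planned | V1, Day -10 to -1 | 1 to 10 days |
| On binders, if V1a carried the test | V1a, Day -10 to -1 | 1 to 10 days |

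The freshest result on the binder route is 19 - 10 = 9 days older than the oldest result on the other route. At matching ends of the windows the difference is 28 - 10 = 18 and 19 - 1 = 18 days.

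**Time from the only scheduled test to V6.** Day 1 to Day 57 is 56 days.

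- On binders: 19 + 56 = 75 to 28 + 56 = 84 days.
- Not on binders: 1 + 56 = 57 to 10 + 56 = 66 days.
- With V6 at Day 60, the upper ends become 84 + 3 = 87 and 66 + 3 = 69 days.

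**Sensitivity to the visit window.** The synopsis allows ± 3 days for all site visits, while Section 10.1 limits this to visits after Day 1. If it also applied to V1, the gap on the binder route would be 19 - 3 = 16 to 28 + 3 = 31 days. The 28-day cap argues against the upper end.

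**Can V1a carry an entry check?** Yes. The V1a phosphorus value decides eligibility (I 02) and the stratum (Section 8.4), so that central laboratory result must already be back before randomization. V2 cannot: its central results lead to the V2a call, which comes after the first dose at the site (Sections 10.1.2.1 and 10.1.2.2).

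**The case against.** The strongest reply is that the protocol relies on prevention and is consistent with itself. E 14 requires willingness to use contraception, and loss of contraception or intention to become pregnant is itself a reason to stop (Section 10.3.3). Contraception methods are source data (Section 10.2). The flow chart and visit lists agree on one test, and nothing in the protocol sets a maximum age for the result. The drug is described as non-absorbed (Sections 4 and 10.4.1.3), and the documents state no embryo-fetal risk.

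Most of this stands. It makes the point one of design rather than contradiction, and it lowers the risk. But contraception rules do not detect a pregnancy, and the protocol tests at V1 despite E 14. The protocol gives pregnancy three consequences of its own, so it cannot treat the matter as unimportant.

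Stronger readings are tempting, and the documents do not support them:

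- *Nobody is tested after V1.* What can be said is that no further test is scheduled. Section 10.1 lets the investigator test relevant laboratory parameters at any visit for a safety concern, and a re-screened woman would repeat V1.
- *Detection on treatment, and hence the AESI count, rests on self-report alone.* Site staff examine and weigh patients and collect adverse events at V2 to V6, and discretionary tests are possible. The AESI also covers partners of male patients, whom no testing of participants would find.
- *A stated share of the 202 patients is affected.* The documents give neither the number of women of childbearing potential nor the share on binders. Any count would be assumed, and the gap before dosing concerns only women who are in both groups.
- *A V6 test would close the gap.* V6 is the end-of-treatment visit, so a result from it could not trigger the stopping rule.

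**Conclusion.** The point holds as a modest safety improvement. One pregnancy test is scheduled, at V1. For women of childbearing potential on binders its result is 19 to 28 days old at first dose, against 1 to 10 days for the others, and E 13 is reviewed twice more without new data. The figures rest on the protocol's own windows and on counting without a Day 0.

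The number of women affected is unknown and no expected number of missed pregnancies can be derived. In the copy reviewed, the column under the flow chart's single mark could not be read; the visit lists place it at V1.

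The absence of a scheduled test during treatment is a second, looser point. It is a mismatch between the test schedule and the rules that depend on detection, and it is for the sponsor to resolve. A reader might infer that the stopping rule cannot work at all. The documents do not support that, because a pregnancy found by any other means still triggers it.

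**What to change.** Add the serum pregnancy test to the V1a blood sample for women of childbearing potential. Mark it in flow chart 1.2 and list it in Section 10.1.1.2. Both entry routes would then have a result from Day -10 to -1 before randomization. This equalizes the two routes; it does not remove the risk of a conception too close to the sample, or after it.

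The cost is one extra assay per such woman on blood already drawn (assuming the sample volume suffices) and a minor amendment. No new visit is needed. The current amendment is dated 13 April 2018 and the first patient was randomized on 21 July 2016 (SAP Section 1.5), so a change would reach only patients not yet past V1a.

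For the treatment period, the sponsor should reconcile the test schedule with the stopping rule in Sections 10.3 and 10.3.3 and with the AESI in Section 10.4.1.3. A V6 assay is optional: it would only make the pregnancy AESI count more complete.
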